**Recruitment procedures.**

At MGH, a research assistant or other study staff member will review lists of potentially eligible patients, and ask providers to introduce the study, and obtain permission to be contacted by a study staff member. Participants may also be directed referred to the study by a health care provider. Flyers advertising the study will also be posted in patient waiting areas in Boston area hospitals (as described above) and health centers and distributed to Boston-area community organizations serving persons living with HIV (e.g., AIDS Action and The Living Center). Rally, the Partners Healthcare online recruitment platform, will also be used to aid in recruitment efforts. Additionally, study staff will use the MGH Research Patient Data Registry (RPDR) to identify patients who meet eligibility criteria and have previously indicated their interest in research participation, and conduct direct patient outreach via letters. The study team will attend meetings of the clinics from which patients are recruited to discuss the study as needed. These

methods have been used successfully in other projects, including [name] University Center for AIDS Research Scholar Award (P30 AI060354) with a similar population, and Phase I of this study (2017P000404).

### **Consent procedures.**

After eligibility has been determined and interest in participation has been verified, participants will be scheduled to attend a baseline assessment (either in person or via Zoom) during which the informed consent document will be reviewed in a private setting.

If the baseline assessment is conducted in person, a detailed consent form will be signed by each participant following an explanation of the study procedures. The consent form will include all study procedures, information about potential risks and benefits of participation, and information regarding who they can contact for further questions. It also will state that participation is voluntary, that participants can refuse to answer any question, that they can withdraw from the study at any time, and that study participation is in no way related to their health care. The participant will also be asked to provide permission to receive a reminder call from a study staff member before each study visit and that it is permissible to leave a message, or if they prefer, to receive a confirmatory email with appointment time and location. We will share the "Partners Required Warning Language for Email Correspondence" if they elect to receive email communication to ensure their full understanding of potential confidentiality risks associated with unencrypted emails. Participants will be given as much time as needed to review the consent form before signing, even if it means postponing the baseline assessment.

If the baseline assessment is conducted via Zoom, study staff will email each participant a copy of the study fact sheet prior to their assessment, and then review the fact sheet in full with the participant via Zoom in order to obtain verbal consent. Verbal consent will be documented in a password-protected participant tracking spreadsheet, which will be saved on the Partners secure shared drive and accessible only to members of the study team. Participants will also be given the option to receive a signed copy of the study fact sheet via email or mail for their personal records.

### **Study procedures and data collection.**

Table 1: Approximate Study Timeline for Phase II

Months	Activity
1-16	

• Conduct of the randomized pilot trial groups.

• Complete all recruitment activities.

17-20	

• Complete all participant activities, including post-treatment assessments and follow-up visits.

• Data analysis and write-up.

An approximate timeline for Phase II of the study is provided in Table 1. We have tailored the existing treatment manual to more specifically meet the needs of older women living with HIV based on the first phase of this study, as well as our prior qualitative work with the same population. The original 3RP intervention consisted of eight, 90-minute weekly group sessions and is described in Table 2. We expanded the number of sessions from 8 to 10 to

accommodate the HIV-specific elements and skills added to the original intervention content. A more detailed description of the intervention modules is provided below.

Table 2: Original Relaxation Response Resiliency Program Chapters and Goals

Chapter Title	Goals

Chapter 1  The Relaxation Response Resiliency Program
	
 
○ Introduce the Relaxation Response Resiliency Program (3RP) and its 3 components
 
○ Discuss how to elicit the RR
 
○ Introduce RR-elicitation method: single pointed focus meditation
 
○ Introduce the concept of appreciation
 
○ Establish program and weekly goals
 
○ Identify individual's sources of stress and coping
 

Chapter 2  The Relaxation Response
	
 
○ Introduce RR-elicitation method: breath awareness
 
○ Describe the relationship between the RR, health and wellness
 
○ Introduce 'Minis' as a method to reduce tension and anxiety through the day
 
○ Assess recuperative sleep
 

Chapter 3  The Four Components of Stress: Emotional and Behavioral
	
 
○ Introduce RR-elicitation method: autogenic training
 
○ Learn the four-component model of stress
 
○ Identify individual's emotional and behavioral components of stress
 


Chapter 4  The Four Components of Stress: Physical and Cognitive
	
 
○ Introduce new RR-elicitation method: chair yoga
 
○ Describe cognitive and physical components of stress
 
○ Describe automatic, self-defeating thoughts
 
○ Define different types of cognitive distortions, and learn how to identify them
 

Chapter 5  Building a Positive Perspective
	
 
○ Introduce new RR-elicitation method: joyful place imagery
 
○ Use cognitive reappraisal as a way to build adaption
 
○ Identify how positivity can increase resiliency in the long term
 
○ Learn concepts and strategies for enhancing positivity
 

Chapter 6  Mindful Awareness and Acceptance
	
 
○ Introduce RR-elicitation method: mindful awareness
 
○ Use strategies for applying mindful awareness in daily living
 
○ Learn about different coping styles: problem-solving and acceptance-based coping
 
○ Explore the development of acceptance, an essential quality of acceptance-based coping
 

Chapter 7  Healing States of Mind
	
 
○ Introduce RR-elicitation method: loving-kindness meditation
 
○ Introduce and evaluate types of social support
 
○ Learn how to select coping strategies: problem-solving and acceptance
 
○ Practice using humor to enhance processes of appreciation and acceptance
 
○ Introduce RR-elicitation method: idealized self
 

Chapter 8 Staying Resilient	

○ Identify how empathy can increase resiliency in the long term

○ Review 3RP strategies learned

○ Develop a plan for continuing to use program strategies

○ Set goals for the future

--	--

Optimizing health can facilitate psychological resilience. Because successful management of HIV requires ongoing contact with the medical system and lifelong adherence to antiretroviral therapy, and because older women with HIV often have to navigate additional medical comorbidities,46,47(p) information on how to manage health in the context of HIV has been added to content from the *“Healing States of Mind”* module, in addition to information on activity and nutrition. We expanded upon the *“Building a Positive Perspective”* content to include material on valued action based on our finding that living a meaningful life and finding meaning from an HIV diagnosis is important to aging well with HIV. The concept of valued action is derived from Acceptance and Commitment Therapy and involves identifying values across multiple domains of life and assessing current satisfaction with each domain.

Our prior data also suggested that capitalizing on positive social supports and minimizing contact with negative social supports is important. Thus, we expanded the content contained in the *“Healing States of Mind”* module to include an exercise that involves identifying positive and negative social influences, and using problem-solving skills to formulate plans to develop greater positive social support, and reduce the impact of negative social influences. Given the data on challenges with sexuality and the high levels of stigma and social isolation in this population, sexuality will also be directly targeted in combination with content from the *“Healing States of Mind”* module. Updated education on risks of HIV transmission (particularly in the era of treatment as prevention and biomedical HIV prevention) will be shared. Goals around sexuality will be discussed, and problem-solving skills will be used to overcome barriers to healthy sexuality.

Throughout the program, participants will set goals for their weekly relaxation practice, in addition to other self-determined goals related but not limited to healthy lifestyle behaviors, HIV management, social support, and valued action. Progress on goals will be evaluated and new goals will be set over time. For example, if an individual articulates that she values service to the HIV community, but is not currently engaged with that community, goals may include researching options for involvement, contacting agencies of interest, and eventually applying to serve as a volunteer.

As described above, some of the most common challenges for older women living with HIV are anxiety, depression, loneliness, managing multiple medical comorbidities, chronic pain, fatigue, sexuality, and stigma. In Table 3, we highlight how the skills contained in our modified 3RP intervention target these issues.

Table 3: Skills Table

Common concerns for older women living with HIV	Current intervention skills	Additional skills added to existing intervention
Stress of managing a chronic long-term, life threatening illness; toxicities associated with long term use of ARVs; additional medical comorbidities	Eliciting the relaxation response (e.g., meditation, chair yoga; imagery); optimizing recuperative sleep; cognitive reappraisal; building a positive perspective; acceptance based coping skills; physical activity and nutrition recommendations	Supporting healthy lifestyle behaviors (e.g., how to manage health in the context of HIV); self-compassion
Pain and fatigue	Eliciting the relaxation response (e.g., meditation, chair yoga; imagery); cognitive reappraisal	Supporting healthy lifestyle behaviors (e.g., pacing); self-compassion
Stigma and social isolation	Evaluation of current social support; cognitive reappraisal; building a positive perspective; acceptance based coping skills	Valued action; problem-solving around developing healthy social supports; self-compassion
Depression and anxiety	Eliciting the relaxation response (e.g., meditation, chair yoga; imagery); cognitive reappraisal; building a positive perspective; acceptance based coping skills; physical activity and nutrition recommendations	Valued action; problem-solving around developing healthy social supports; self-compassion
Sexuality concerns	Cognitive reappraisal	Education around HIV prevention; development of sexuality goals; problem-solving barriers to goals; self-compassion

In the present phase of this study, we will conduct a randomized pilot of the revised intervention and all assessments among groups of up to 10 participants. Prior to beginning the revised intervention, participants will complete a baseline assessment lasting approximately 45-60 minutes (either in person or via Zoom). At the baseline assessment visit, participants will complete a series of quantitative self-report measures (described below), including sociodemographic information and data on resilience, antiretroviral adherence, stress reactivity, HIV disclosure status, anxiety, depression, social support, health-related quality of life, symptom distress, coping, substance use, perceptions of HIV stigma, and sexual functioning and communication. Participants will also complete a cognitive assessment. All questionnaires will be completed on either a touchscreen tablet or on paper (if the assessment is conducted in person) or verbally via phone or directly in REDCap (if the assessment is conducted via Zoom). For participants for whom questionnaires must be read aloud, response option cards will be provided (either in person or via email) for each instrument to serve as a visual reminder of the response options for scales on different questionnaires. Study staff will be available to assist in completion of the self-report questionnaires when needed. Participants will also be asked to have their blood drawn at the MGH Clinical Research Center (CRC), located in the White

Building 12 on the main hospital campus. In order to minimize inconvenience, participants will be provided with information about the on-call MGH shuttle service that can transport them to the main hospital campus from [name]. All blood draws are optional; participants may opt out and still participate in the study. Note: Study blood draws will not be conducted for the duration of virtual conduct of study procedures (i.e., assessment visits and group sessions). If and when it becomes safe for participants to receive blood draws in-person, scheduling of study blood draw visits will resume.

If participants who have completed a baseline assessment are unable to participate in the group (e.g., due to changes in availability), study staff will re-do the informed consent process and baseline assessments before participants join a subsequent group.

Following completion of this initial baseline visit, participants will be randomized (1:1) to the intervention or control arm. Random assignment to condition will minimize the likelihood of bias in either condition. A study research assistant or staff member not involved in the actual therapy will hold the randomization scheme, which will be developed by the study biostatistician ([name]). Baseline characteristics for each group will be examined for significant differences.

The control condition will be a supportive therapy program that is matched to the intervention for number and length of sessions. A version of this intervention has been used in a randomized controlled trial evaluating the efficacy of a combined depression and adherence treatment intervention, on which [name] worked (R01MH084757). Basic principles of supportive psychotherapy will be followed, and the interventionist will facilitate discussion around what it is like to live with HIV as an aging woman. Sessions will be delivered by a study staff member (either in person or via Zoom) who will be thoroughly trained on the intervention or control condition material (e.g., predoctoral psychology intern, postdoctoral psychology fellow, junior psychologist). All group facilitators will receive supervision on a weekly or biweekly basis.

Participants will be given the opportunity to attend up to 3 make-up sessions (either in person or via Zoom) if they are unable to attend the originally scheduled session. For the control condition, makeup sessions will entail individual supportive psychotherapy. We will also allow participants to call into up to 3 group sessions by phone after having attended at least one session in-person. This will allow for more flexibility in scheduling and facilitate better overall attendance over the duration of the program. Additionally, participants in both the intervention and control groups will receive a schedule of all group sessions in order to minimize confusion about session dates and maximize efficiency of make-up scheduling.

Following completion of the intervention or the control group sessions, participants will complete a post-treatment assessment (either in person or via Zoom). Apart from the sociodemographic information, participants will complete all the same quantitative self-report measures (described below) as in the baseline assessment. Additional measures assessed at post-treatment include a measure of client satisfaction and a measure of perceptions regarding study assessments. All questionnaires will be completed on either a touchscreen tablet or on paper as described above (if the assessment is conducted in person) or verbally via phone or directly in REDCap (if the assessment is conducted via Zoom). We will also conduct semi-structured, individual qualitative exit interviews (either in person or via Zoom) to evaluate participants' perceptions of their experience in the study. Interviews will explore treatment content, satisfaction with group format (including group versus individual delivery), length of individual sessions, scheduling and location of sessions, adherence to the skills covered in the sessions, length of the overall group intervention, and perceptions of the assessment experience, including length of battery. In

addition to the qualitative interviews, the randomized pilot trial will provide information relevant to manual revisions in the form of audio recordings of sessions, weekly progress notes, therapist and patient ratings of satisfaction with and helpfulness of treatment procedures, and participant ratings of out of session practice of skills. Audio recordings of selected sessions will be made available for download from a secure, password-protected, HIPAA-compliant website and viewed by the study team.

Finally, we will conduct 3-month follow-up assessments (either in person or via Zoom), during which participants will complete all the same quantitative self-report measures (described below) as in the post-treatment assessment, apart from the sociodemographic information, client satisfaction measure, and measure of perceptions regarding study assessments. All questionnaires will be completed on either a touchscreen tablet or on paper as described above (if the assessment is conducted in person) or verbally via phone or directly in REDCap (if the assessment is conducted via Zoom).

**Retention.** The research assistant will track participant retention, which will be reviewed weekly by the principal investigator. We will collect extensive locator information at baseline (that contains contact information for at least two individuals with whom the participant is in regular contact) for participants in the event that they move or discontinue HIV care at the recruitment site, or become lost to follow-up from study procedures. Locator form information will be collected either in person or via Zoom. Should the individuals listed on the locator form be contacted, reference to HIV will never be made. We will make concerted efforts to maintain contact with individuals who discontinue the intervention but are still willing to complete follow-up assessments. To facilitate such retention, if necessary we will meet with participants at any confidential location that is comfortable for them for study assessment visits. Additionally, we have budgeted for financial incentives and public transportation costs.

**Fidelity:** All sessions led by the group facilitators will be audio-taped. Monitoring of the intervention will take into account both therapist adherence as well as competence. We have developed a rating checklist for therapist adherence including whether the specific components of the modules of treatment were delivered, as well as a contamination checklist to measure the degree to which group facilitators introduced intervention content into the control sessions. This will be done by the PI ([name]) or clinical supervisor. At least ten percent of the sessions will be reviewed.

**Assessment instruments:** All assessments that occur post treatment will be conducted by a study team member who did not serve as the group facilitator to minimize the risk of bias. We expect the baseline assessment, post-treatment assessment, and 3-month follow-up assessment to each last approximately 45-60 minutes.

**Sociodemographic data:** Data on age, race/ethnicity, relationship status, occupational status, and socioeconomic status will be collected at baseline, as will disclosure of HIV status and history of exposure to traumatic events, including interpersonal violence. Participant zip codes will also be recorded to account for time traveled to study visits.

**Feasibility:** To assess feasibility, we will track the number of potential participants we screen, the number of potential participants who meet study inclusion criteria, the number of participants who meet study criteria and then enroll (and the time it takes to complete these steps), and the number of treatment and assessment sessions completed by all enrolled participants. We will also track the duration of assessments, reasons for declining enrollment and for prematurely leaving the trial, and make-up sessions attended. The study team will review these data and

determine the degree of feasibility, though we will consider these feasibility/retention outcomes in the context of what other trials conducted with older individuals living with HIV have achieved.

Acceptability: Acceptability will be assessed at post treatment using the eight-item Client Satisfaction Questionnaire (CSQ-8), a measure of how much an individual values a treatment. Items assess factors such as the perceived quality of the services, how much the services met needs, satisfaction with the help received, and others. Items are scored from 1 (poor) to 4 (excellent), with higher scores indicating greater satisfaction. We will also ask participants about their perceptions of the burden of the study assessment battery.

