*Cognitive status:* Cognitive status will be assessed using the Mini-Cog. The Mini-Cog can quickly detect cognitive impairment through its three-item recall test and a clock-drawing test (CDT) administered by a clinician. Respondents score as positive for cognitive impairment if they recall no words, or recall 1 or 2 words with an abnormal CDT. Both measures have been used with older adults in various health care settings, and previous research has found consistently good reliability and validity.

*Weekly adherence to skills:* Practice notes have been developed to correspond with each module of the 3RP treatment. Participants will be asked to keep brief daily diaries of their out of session practice (e.g., completion of 15 minutes of meditation, engaged in activities to foster social connectedness, engaged in a desired lifestyle behavior, etc.). These diaries will be used to generate a rating of adherence to out of session practice guidelines. If group sessions are conducted virtually via Zoom, participants in the intervention group will be mailed an envelope

containing weekly practice notes to be completed during the 10-week group program. Participants will then be asked to mail back the completed practice notes (via a pre-paid envelope) at the end of the program.

*Treatment Credibility and Expectancy:* The Treatment Credibility/Expectancy Questionnaire (CEQ) is a widely used 6-item measure that assesses treatment credibility and expectancy. Participants are asked to rate the treatment from 1 (not at all) to 9 (very much) and from 0% (not at all) to 100% (very much). The percentage ratings are subjected to linear transformation with a minimum of 1 and a maximum of 9. We will administer the scale after the first treatment session.

*COVID-19-related:* Quantitative assessments and the qualitative exit interview will contain COVID-19-related items in order to better understand the impact of COVID-19 and corresponding public health restrictions on participants' lives (e.g., mental health, ability to adhere to HIV medications), and their experience participating in this study.

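### Post-treatment assessors need only not have been the group facilitator: nothing keeps them unaware of arm or separates them from the holder of the randomization scheme

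*Combined protocol and SAP*

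**What the plan says.** The rule on assessors is in the Assessment instruments paragraph of Research Strategy: "All assessments that occur post treatment will be conducted by a study team member who did not serve as the group facilitator". Its stated purpose is to reduce bias.

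Earlier in the same section, after the baseline visit, "participants will be randomized (1:1) to the intervention or control arm". Custody of the list is then assigned: "A study research assistant or staff member not involved in the actual therapy will hold the randomization scheme".

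On how measures are taken, the baseline description says "For participants for whom questionnaires must be read aloud, response option cards will be provided" and "Study staff will be available to assist in completion of the self-report questionnaires when needed". For in-person visits, the post-treatment and 3-month descriptions refer back to that text. For remote visits they offer completion "verbally via phone or directly in REDCap (if the assessment is conducted via Zoom"). The Mini-Cog, listed under Secondary Outcomes: HIV/Physical Health, includes a "clock-drawing test (CDT) administered by a clinician".

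The exit interview covers what the treatment contained and how far participants kept up the skills taught.

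**The concern.** The rule aims at bias but removes only one person, the facilitator. An assessor who did not lead the group may still know the arm, and nothing stops the holder of the allocations from running outcome visits.

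Participants cannot be masked to a group talking therapy, but the person collecting their outcomes can be. An assessor who knows the arm can, without intending it, prompt differently or invite agreeable answers when reading items aloud or taking them by phone. The Specific Aims predict greater improvement under the adapted 3RP, and both the aims and the SAP say the team wants to learn whether its measures respond to change. Differential prompting would look like such a response. The funder text quoted in the SAP also describes this type of grant as the place to work out the assessment protocol and randomization procedures. As written, the trial would not show whether assessors can be kept masked.

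**Working it through.** No arithmetic in the plan bears on this point. The check compares the role definitions and procedures.

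1. **Who may assess.** An assessor is any team member who was not the group facilitator. The list holder is any research assistant or staff member uninvolved in the therapy. Someone uninvolved in the therapy cannot have been the facilitator, so every permitted list holder also meets the assessor rule. The rule speaks of the facilitator in the singular, so it is also unclear whether the facilitator of another group is excluded.

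2. **Any other rule.** Research Strategy, the data analytic plan, Data monitoring, staff training and the SAP contain no statement that assessors are masked, no bar on the list holder assessing, and no requirement to record unmasking. The nearest provisions are weekly data verification by a research assistant with no data-collection role or participant contact (Data monitoring) and training in assessment and interviewing (Minimization of risks). The first checks data already recorded. The second may limit prompting. Neither conceals the arm.

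3. **Ordinary routes to knowing the arm.** The research assistant tracks retention, and make-up sessions are tracked. Control make-ups are individual supportive psychotherapy. When groups meet by Zoom, practice notes are mailed to the intervention arm. The study team may review session recordings. Non-facilitating staff could therefore learn the arm without seeing the list.

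4. **Where the assessor can affect a result.**

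| Mode or measure | Assessor's part |
|---|---|
| Self-completion on tablet, paper or in REDCap | Small, unless help is given |
| Read aloud in person | Direct, but only for participants who need it |
| Verbal by phone at remote visits | Direct; no default between this and REDCap entry |
| Mini-Cog | Direct, if repeated |
| Viral load | None (laboratory result) |

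5. **Is the Mini-Cog repeated?** The baseline description lists a cognitive assessment separately from the self-report measures. The post-treatment and 3-month descriptions repeat only the self-report measures. The Specific Aims list improved cognitive status among the secondary outcomes, which implies repetition. Table 4, the assessment timeline, is not in the text available for this review, so the point stays conditional.

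6. **Order of procedures.** Nothing places the outcome measures before the exit interview or requires a different interviewer. If the interview came first with the same person, its subject matter could disclose the arm.

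7. **Extent.** With up to 60 women and two post-baseline assessments each, 60 × 2 = 120 visits at most fall under the rule. This assumes no attrition and counts self-completed visits, so it is a ceiling on visits covered, not a count of visits affected. The split by mode is not given.

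**The case against.** The strongest reply is that assessor masking would leave the main source of bias in place. Most outcomes are the participant's own ratings, and she knows which sessions she attended. In-person forms are normally self-completed, with reading aloud and staff help reserved for those who need them. The primary aim is feasibility and acceptability, outcome analyses are exploratory, and the SAP disclaims using the data to estimate an effect size. All of this stands and limits the point's importance. It does not close the gap for verbally completed measures, or for sensitivity to change, which the team does want to judge.

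Four stronger readings are tempting, but the documents do not support them:

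- **That the list holder or another group's facilitator will assess.** The text permits the first and leaves the second unclear; it plans neither.
- **That the list holder will score the Mini-Cog after treatment.** Repetition is only implied, administration is by a clinician, and no passage says who scores the test or that this clinician holds the list.
- **That the satisfaction questionnaire reveals the arm.** The plan says "Additional measures assessed at post-treatment include a measure of client satisfaction", but the items described concern service quality, needs met and satisfaction, which do not identify a treatment. The exit interview is the more plausible route.
- **That the bias can be sized from the power section.** An assumed shift of 0.1 to 0.2 SD, set against the SAP's detectable between-arm difference of 8.7 / 11.8 = 0.74 SD, gives 0.1 / 0.74 to 0.2 / 0.74, or about 14% to 27%. The result only restates the assumption, for which the documents give no basis. Converting it to points (0.1 × 11.8 = 1.2 to 0.2 × 11.8 = 2.4) is worse: the SAP quotes reference means of 71.7 and 76, while the protocol's CD-RISC runs from 0 to 40, so those figures do not fit the trial's scale.

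**Conclusion.** The point holds as a weakness in a stated safeguard. The rule falls short of its own aim: it neither keeps assessors unaware of arm nor separates them from the allocation list. The exposure is confined to measures taken verbally, read aloud or completed with help, and to the Mini-Cog if it is repeated.

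The size of any bias cannot be derived from the documents. Correcting the rule is worthwhile but modest: it would make the judgement of sensitivity to change more trustworthy and show whether masking is workable in a larger trial.

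The conclusion assumes that no masking rule sits in a manual or in Table 4, and that the read-aloud and assistance provisions written for baseline carry over to later visits, as the cross-reference suggests for in-person visits.

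**What to change.** Replace the assessor sentence under Assessment instruments with wording to this effect:

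> Post-treatment and 3-month outcome measures are administered by a team member who facilitates no study group, does not hold the randomization scheme and, where possible, has not been told the participant's arm. Participants are asked not to disclose their group. At remote visits, direct entry in REDCap is the default and verbal completion is used only when needed. The exit interview follows all outcome measures or is conducted by another person. The assessor records the mode of administration and whether the arm became known.

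State also whether the Mini-Cog is repeated after baseline. If it is, apply the same conditions to the clinician who gives it.

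The change needs protocol wording and a reallocation of duties within existing staff. The plan already has a research assistant with no data-collection role, so separating duties appears feasible. The cost is less flexible scheduling in a small team, and some unmasking will remain. Recording it turns that limitation into feasibility information for the full-scale trial.
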